Published data in support of evaluating cAd3 vectors for a next generation Marburg vaccine comes from the Phase I, dose-escalation, open-label trial of cAd3-EBO performed by Ledgerwood, *et al.* [16]. Twenty healthy adults, sequentially enrolled in two groups of 10, received IM doses of 2×10^{10} particle units or 2×10^{11} particle units. No safety concerns were identified although, transient fever developed within 1 day after vaccination in two participants in the high dose group. Glycoprotein-specific antibodies were induced in all 20 participants, however the high dose group developed antibodies of higher magnitude and more frequent CD4 and CD8 T cell responses to vaccine antigen. Other studies evaluating this product in U.S., Swiss

and Malian adults showed the Ebola cAd3 vaccine to be safe and immunogenic [16-19]. Similar cAd3 Marburg GP doses will be tested in this slowly enrolling, staged, dose-escalation study.

In summary, use of the recombinant, non-replicating cAd3 vector for construction of the cAd3-Marburg vaccine is based on its properties to induce immune responses as readily as rAd5, but with little to no pre-existing immunity in human populations. The encoded WT GP antigens were chosen based on preclinical data and may provide protective immunity against Marburgvirus species and on their demonstrated safety in humans when expressed by a DNA plasmid.

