Participants will be given a “Diary Card”, a thermometer, and a ruler. The diary card will be used as a memory aid, on which the participant will record temperature, local and systemic symptoms and concomitant medications daily for 7 days after the injection. Participants will be trained to complete the paper diary card, how to use the thermometer, and how to measure injection site swelling and redness using the ruler. Completion of the diary card training will be noted in source documents. The written (paper) diary card will be transcribed into the study database and will be stored in the participant file for monitoring purposes.

The solicited signs and symptoms on the diary card (among others) will include: joint pain, unusually tired, muscles aches (other than at injection site), headache, chills, nausea, and pain at injection site. Participants will also record the day’s highest measured temperature and measurement of largest diameter for redness and swelling at the injection site. The completed diary cards are collected at the first visit following completion of the 7-day diary card (about 2 weeks after the injection).

Follow-up on participant well-being will be performed by telephone or clinic visit on the day following vaccination and by clinic visit on Day 3 following the injection to assess their clinical status. Participants may call or come to the clinic at any time-point for evaluation, if they experience unusual, moderate or severe signs and symptoms. Diary cards will be reviewed with the clinician at any visit from day of vaccination through the first study visit following completion of the diary card. If upon reviewing the clinician finds that general symptom or injection site symptom information (except swelling or redness measurements) is missing from the diary cards, the participant will be asked to provide the missing information to the best of their recollection.

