5.2.2. Management of Reactogenicity and Other Adverse Events

Events following injection that may require clinical evaluation include a fever of 38.5°C/101.3°F (Grade 2) or higher lasting greater than 24 hours, rash, urticaria, or significant impairment in the activities of daily living (ADL). Fever of any severity or any condition which in the judgment of

the clinician should be evaluated would require a clinical visit. Participants are permitted to initiate an unscheduled clinic visit at their discretion but these visits will be compensated as per Section 11.5.

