11.3. Risks

11.3.1. Risks of the cAd3-Marburg Vaccine

Potential side effects resulting from intramuscular injection include pain, stinging, arm discomfort, redness of the skin or mild bruising at vaccine injection sites. Study participants can receive medications such as acetaminophen, NSAIDs, or antihistamines as required.

Participants may exhibit general signs and symptoms associated with administration of a vaccine including fever, chills, rash, aches and pains, nausea, headache, dizziness and fatigue. These side effects will be monitored, but are generally short term and do not require treatment. As with all vaccines, an allergic reaction is possible and will be managed as per site SOP for anaphylaxis. To mitigate this risk, participants will be observed in the clinic for 30 or 60 minutes post-injection.

Chimpanzee adenoviral vector vaccines have been generally safe in healthy adults at dosages up to 10^{11} PU per injection in completed and ongoing clinical trials [16, 23, 24]. Systemic reactogenicity typically occurs on the day of or day after vaccination and may include headache, malaise, myalgia, chills, and fever. When present, fever onset occurs within 1 day of vaccination and typically resolves within 24 hours of onset. A pattern of fever occurring later than 1 day after vaccination or lasting longer than 1 day may require evaluation for additional etiology.

Risks of the vaccine to pregnant and nursing women and to the unborn fetus are unknown.

There may be other unknown side effects.

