| ⁴ Fever (°C) (°F) | 38.0 – 38.4 100.4 – 101.1 | 38.5 – 38.9 101.2 – 102.0 | 39.0 – 40 102.1 – 104 | > 40 > 104 |
| Tachycardia - beats per minute | 101 – 115 | 116 – 130 | > 130 | Hospitalization for arrhythmia |
| ⁵ Bradycardia - beats per Minute | 50 – 54 | 45 – 49 | < 45 | Hospitalization for arrhythmia |
| Hypertension (systolic) - mm Hg | 141 – 150 | 151 – 155 | > 155 | Hospitalization for malignant hypertension |
| Hypertension (diastolic) - mm Hg | 91 – 95 | 96 – 100 | > 100 | Hospitalization for malignant hypertension |
| Hypotension (systolic) – mm Hg | 85 – 89 and symptomatic | 80 – 84 and symptomatic and requiring oral fluids | < 80 and symptomatic and requiring IV fluids | Hospitalization for hypotensive shock |
| Respiratory Rate – breaths per minute | 17 – 20 | 21 – 25 | > 25 | Intubation |

1. In addition to grading the measured local reaction at the greatest single diameter, the measurement should be recorded as a continuous variable.
2. Induration/Swelling should be evaluated and graded using the functional scale as well as the actual measurement.
3. Subject should be at rest for all vital sign measurements.
4. Oral temperature; no recent hot or cold beverages or smoking.
5. When resting heart rate is between 60 – 100 beats per minute. Use clinical judgment when characterizing Bradycardia among some healthy subject populations, for example, conditioned athletes.

| Systemic (General) | Mild (Grade 1) | Moderate (Grade 2) | Severe (Grade 3) | Potentially Life Threatening (Grade 4) |
|---------------------------|--|--|--|---|
| Nausea/vomiting | No interference with activity or 1 – 2 episodes/24 hours | Some interference with activity or > 2 episodes/24 hours | Prevents daily activity, requires outpatient IV hydration | Hospitalization for hypotensive shock |
| Diarrhea | 2 – 3 loose stools or < 400 gms/24 hours | 4 – 5 stools or 400 – 800 gms/24 hours | 6 or more watery stools or > 800gms/24 hours or requires outpatient IV hydration | Hospitalization |
| Headache | No interference with activity | Repeated use of non-narcotic pain reliever > 24 hours or some interference with activity | Significant; any use of narcotic pain reliever or prevents daily activity | Hospitalization |
| Fatigue | No interference with activity | Some interference with activity | Significant; prevents daily activity | Hospitalization |

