APPENDIX 13: DIARY CARD

WRAIR

Walter Reed Army
Institute of Research

Soldier Health • World Health

RV 507 Participant Diary Card

Walter Reed Army Institute of Research
Clinical Trials Center

Version 1.7
13 February 2019

Participant ID

Walter Reed Army Institute of Research
Clinical Trials Center
[name]
[name] 20910
[contact]
After Work Hours: [contact]

Participant ID

Symptoms Severity Scale

None = you have no symptoms

Mild = minimal symptoms; cause minimal or no interference with work, school, or self care activities.

Moderate = notable symptoms; required modification in activity or medication; did not result in loss of work or cancellation of social activities

Severe = incapacitating symptoms; requiring bed rest and/or resulted in loss of work or cancellation of social activities.

**For any Problems Call:
[contact] OR [contact]**

Injection Site Pain Severity Scale

None = no pain

Mild = minimal pain; no limitation of use of arm.

[figure not shown]
[figure not shown]
[figure not shown]
Moderate = notable pain; some limitation of use of arm.

Severe = extreme pain; complete limitation of use of arm.

How to Measure Swelling and Redness at the Injection Site

1. Determine the widest part (or diameter) of the area.
2. Using the ruler that the clinic staff gave to you, measure the widest part of the area in centimeters (cm) as shown on the pictures below. Each small hash mark on the centimeter ruler equals one tenth (0.1) of a centimeter.
3. Measure the swelling (raised area) and the redness (red area) separately and record each measurement on the diary card.

Please complete this diary in black or blue ink only

Participant ID

Day of Vaccination

Date: ____/____/____ (dd/mmm/yyyy)

The evening of the day of Vaccination:

Temp: _____ (oral, °F) Time Taken: _____ PM

If you have a fever and wish to take your temperature again, record your additional temperature:

Temp: _____ (oral, °F) Time Taken: _____ AM / PM (circle)

Temp: _____ (oral, °F) Time Taken: _____ AM / PM (circle)

Are you taking any medication? Yes No

If yes, please list medication(s):

Please use the symptom scale at the bottom of the page

| Gen. Symptoms | None | Mild | Moderate | Severe |
|--------------------------------------|------|------|----------|--------|
| Joint Pain | | | | |
| Unusually Tired | | | | |
| Muscle Aches (not at injection site) | | | | |
| Headache | | | | |
| Chills | | | | |
| Nausea | | | | |

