| Injection Site Symptoms | None | Mild | Moderate | Severe |
|---------------------------|--------------|------|---|--------|
| Local Pain | | | | |
| Swelling Measure in cm | ____.____ cm | | Please record in cm, the largest width measurement of the swelling (Example: 2.5 cm) | |
| Redness Measure in cm | ____.____ cm | | Please record in cm, the largest width measurement of the redness (Example: 2.5 cm) | |

Symptoms Severity Scale**None** = no symptoms**Mild** = minimal symptoms; cause minimal or no interference with work, school, or self-care activities.**Moderate** = notable symptoms; required modification in activity or medication; did not result in loss of work or cancellation of social activities.**Severe** = incapacitating symptoms; requiring bed rest and/or resulted in loss of work or cancellation of social activities.**For any problems call: [contact] OR [contact]****Injection Site Pain Severity Scale****None** = no pain**Mild** = minimal pain; no limitation of use of arm**Moderate** = notable pain; some limitation of use of arm**Severe** = extreme pain; complete limitation of use of arm

Participant ID

Day 1 after Vaccination

Date: ____/____/____ (dd/mmm/yyyy)

Temp: _____ (oral, °F) Time Taken: _____ AM / PM (circle)

If you have a fever and wish to take your temperature again, record your additional temperature:

Temp: _____ (oral, °F) Time Taken: _____ AM / PM (circle)

Temp: _____ (oral, °F) Time Taken: _____ AM / PM (circle)

Are you taking any medication? Yes No

If yes, please list medication(s):

Please use the symptom scale at the bottom of the page

| Gen. Symptoms | None | Mild | Moderate | Severe |
|--------------------------------------|------|------|----------|--------|
| Joint Pain | | | | |
| Unusually Tired | | | | |
| Muscle Aches (not at injection site) | | | | |
| Headache | | | | |
| Chills | | | | |
| Nausea | | | | |

| Injection Site Symptoms | None | Mild | Moderate | Severe |
|---------------------------|--------------|------|--|--------|
| Local Pain | | | | |
| Swelling Measure in cm | ____.____ cm | | Please record in cm, the largest width measurement of the swelling (Example: 2.5 cm) | |
| Redness Measure in cm | ____.____ cm | | Please record in cm, the largest width measurement of the redness (Example: 2.5 cm) | |

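### The diary card can miss short fevers in the first day after vaccination, and the printed °C and °F fever grades disagree by 0.1 °F at two edges

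*Combined protocol and SAP*

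**What the plan says.** **Measurement.** Section 5.2.1 has temperature taken in clinic before injection and at least 30 minutes after it, then recorded daily by the participant for 7 days. It asks for the day's "highest measured temperature and measurement of largest diameter" of redness and swelling, but does not say when or how often to take a temperature. On the card (Appendix 13) the Day 0 reading is tied to "The evening of the day of Vaccination". From Day 1 each page has one temperature line in °F with AM or PM to circle, then two more lines under the prompt "If you have a fever and wish to take your temperature again, record your additional temperature".

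**Expected course.** Section 11.3.1: "When present, fever onset occurs within 1 day of vaccination and typically resolves within 24 hours of onset". Section 1.2.2 reports from the cited trial of the related Ebola vaccine that "transient fever developed within 1 day after vaccination in two participants in the high dose group".

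**Contacts.** Section 5.2.1 allows the Day 1 follow-up by telephone or clinic visit. Appendix 5 lists it as a phone contact with a visit if needed. Appendix 1 marks vital signs in the Day 1 column but gives a daily blood volume of 0 mL there, which fits a phone contact. The next planned visit is Day 3.

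**Grading.** The Appendix 9 fever row starts Grade 1 at 38.0 °C / 100.4 °F. Its Grade 2 and Grade 3 bands are "38.5 – 38.9 101.2 – 102.0 | 39.0 – 40 102.1 – 104", and Grade 4 is above 40 °C / 104 °F. Section 5.2.2 refers to "a fever of 38.5°C/101.3°F (Grade 2) or higher lasting greater than 24 hours". Section 8.3.2 counts each participant once, at maximum severity over all assessments. Section 7.4 pauses the study when two or more participants have the same related Grade 3 or 4 event.

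**The concern.** Fever is a solicited sign and so part of the primary safety endpoint. The protocol expects it to be early and brief, yet the only required home thermometer reading on the day after vaccination comes at whatever hour the participant chooses. The prompt to measure again reaches only someone who already believes they have a fever, and the card does not say what counts as one. A fever that falls between readings is absent from the reactogenicity table. It also cannot prompt the clinical visit that section 5.2.2 attaches to fever of any severity.

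The grading mismatch is a separate and smaller matter. The upper of the two affected edges is the start of Grade 3, which feeds the pause rule, and no section says which unit's bands apply.

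**Working it through.** **1. Grade limits.** With °F = 1.8 × °C + 32:

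| Limit | °C printed | °F printed | °F computed |
|---|---|---|---|
| Grade 1 starts | 38.0 | 100.4 | 100.4 |
| Grade 2 starts | 38.5 | 101.2 | 101.3 |
| Grade 3 starts | 39.0 | 102.1 | 102.2 |
| Grade 4 above | 40 | 104 | 104.0 |

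The first and last rows reproduce; the middle two do not. The 101.3 °F in section 5.2.2 is the exact conversion of 38.5 °C, but it conflicts with the 101.2 °F in Appendix 9.

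Every reading from 99.0 to 105.9 °F in steps of 0.1 was graded on the °F bands, then converted to °C, rounded to 0.1 and graded on the °C bands. Exactly two change:

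- 101.2 °F: (101.2 − 32) × 5/9 = 38.44 °C, Grade 2 on °F and Grade 1 on °C.
- 102.1 °F: (102.1 − 32) × 5/9 = 38.94 °C, Grade 3 on °F and Grade 2 on °C.

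The Grade 3 band holds 20 steps of 0.1 °F, of which one is affected. In the other direction, no 0.1 °C reading from 37.0 to 41.9 changes grade.

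**2. Detection of a short fever.** The documents give neither fever durations nor reading times, so all of the following is assumed: vaccination uniform over 09:00–15:00; onset uniform over the next 24 h; Day 0 reading 18:00–22:00; Day 1 and Day 2 readings 07:00–22:00; no voluntary or clinic readings. A fever of length L is detected if a reading falls between onset and onset + L.

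The 6 h case can be done by hand. Each reading catches the onsets in the 6 h before it, so add up the expected hours of the 24 h onset window that are covered.

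- Day 0 evening: 6 h, less the part falling before vaccination. That loss is (3³/6)/(4 × 6) = 0.1875 h, leaving 5.8125 h.
- Day 1 at a free hour: if the reading's clock hour is no later than the vaccination hour (mean probability 5/15), all 6 h count, giving 2.0 h. Later readings add the integral of (6 − x)/15 from 0 to 6, which is 1.2 h. Total 3.2 h.
- Day 2: the earliest reading is at least 16 h after the latest onset, so it adds nothing for a 6 h or 12 h fever.

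Printed card: (5.8125 + 3.2)/24 = 37.6%.

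With a waking reading (assumed 06:00–08:00) and an evening reading (18:00–22:00) on Day 1, the waking reading covers a full 6 h and the evening one covers 0.1875 h: (5.8125 + 6 + 0.1875)/24 = 50.0%.

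Simulation under the same assumptions (2,000,000 episodes) agrees and gives the longer durations. The second row also has an evening reading on Day 2, which does not alter its results:

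| Fever length | 6 h | 12 h | 18 h | 24 h |
|---|---|---|---|---|
| Printed card | 38% | 69% | 87% | 96% |
| Waking + evening on Day 1 | 50% | 94% | 100% | 100% |
| Gain in points | 12 | 25 | 13 | 4 |

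**The case against.** The strongest reply is that the card captures more than its required lines suggest. Each page has three temperature lines, participants are trained on the thermometer, and people who feel feverish tend to measure. There are clinic temperatures on Day 0 and at later visits, and severity is the maximum over all assessments. This stands in part. Voluntary re-measurement narrows the gap by an amount the documents do not let one estimate. The planned clinic readings do little in the expected window, because they fall shortly after injection and then on Day 3.

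On grading, the diary is in °F only and Appendix 9 prints °F bands. Applying them directly gives one grade per diary reading. Section 5.2.2 concerns clinical evaluation, while sections 7.1 and 7.2 assign grading to Appendix 9. This also stands: a grade changes only if a °F reading is converted first. What remains is that no section says so, and the two sections print different °F values for Grade 2.

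Several stronger readings are tempting but unsupported:

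- *Fever counts depend on the unit.* They do not, because 38.0 °C equals 100.4 °F exactly.
- *The card detects only 25% to 50% of fevers lasting 6 to 12 h.* That follows from one reading per 24 h at a random hour (6/24 and 12/24), which ignores the fixed Day 0 evening reading.
- *About 20% of the high-dose group will have fever.* The 2 of 10 in the cited trial received 2×10^11 PU, twice the high dose here.
- *Capture will differ between the groups.* Both use the same card, and nothing in the documents shows a difference.
- *Antipyretic use should be counted with fever.* Medication is already recorded daily, and such a row would count analgesics taken for headache or arm pain as fever.

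**Conclusion.** Two modest points hold. First, the required readings leave room to miss a short fever in the period when the protocol expects it. Under the stated assumptions a second required Day 1 reading raises detection by about 12 points for a 6 h fever and 25 points for a 12 h fever, falling to 4 points at 24 h. The size rests on assumed reading times, uniform onset and no voluntary readings; if most fevers last close to a day, little is lost.

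Second, Appendix 9 contradicts itself by 0.1 °F at the Grade 1/2 and Grade 2/3 edges, and section 5.2.2 contradicts Appendix 9 at Grade 2. The reach is narrow: readings of exactly 101.2 °F or 102.1 °F, and only on conversion to °C. The second of these lies at the Grade 3 edge used by the pause rule, and would count there only if the event were judged related. Neither point undermines the trial. Both are worthwhile refinements.

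**What to change.** 1. On the Day 1 page of the diary card, print two required readings with times, one on waking and one in the evening. Keep the optional lines. State in section 5.2.1 when the readings are taken, and analyse the day's highest. The cost is one more line, one database field, IRB approval of the revised card and a small added burden for participants.
2. Reconcile section 5.2.2 with the fever row of Appendix 9, and state which unit's bands govern grading and the pause rule. This is a text correction. Which cut-off is right is for the sponsor and investigators to settle, and this review takes no position on it.
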